4.1.2 Rationale for Atezolizumab Starting Dose and Schedule

The dose of atezolizumab will be 1200 mg IV on Day 1 (+/-2 days) of each 21-day cycle.

The atezolizumab dose is informed by available clinical activity, safety, PK, and immunogenicity data. Anti-tumor activity has been observed across doses from 1 mg/kg to 20 mg/kg administered q3w. The MTD of atezolizumab was not reached and no DLTs have been observed at any dose in Study PCD4989g. Available preliminary PK data (0.03–20 mg/kg) from Study PCD4989g suggest that for doses \geq 1 mg/kg q3w, overall, atezolizumab exhibits pharmacokinetics that are both linear and consistent with typical IgG1 antibodies. Detectable ATAs were observed in patients at all dose levels but were only associated with changes in pharmacokinetics for patients in the lower dose cohorts (0.3, 1, and 3 mg/kg). It is unclear from currently available data in these lower dose cohorts if administration of higher doses to patients with both detectable ATAs and reduced exposure would restore exposure to expected levels. No clear relationship between the development of measurable

ATAs and safety or efficacy has been observed. Available data suggest that development of detectable ATAs does not appear to have a significant impact on pharmacokinetics in most patients at doses of 10 to 20 mg/kg administered q3w. Correspondingly, patients dosed at the 10-, 15-, and 20-mg/kg q3w dose levels have maintained target trough levels of drug despite the detection of ATAs.

Currently available PK and ATA data suggest that the 15-mg/kg atezolizumab q3w regimen (equivalent to the 1200-mg q3w fixed dose) for Phase II and Phase III studies would be sufficient to both maintain $C_{trough} \geq 6 \mu\text{g/mL}$ and further safeguard against both interpatient variability and the potential effect of ATAs that could lead to subtherapeutic levels of atezolizumab relative to the 10-mg/kg atezolizumab q3w regimen (or fixed-dose equivalent). From inspection of available observed C_{trough} data, moving further to the 20-mg/kg atezolizumab q3w regimen does not appear to be warranted to maintain targeted C_{trough} levels relative to the proposed 15-mg/kg atezolizumab q3w level.

Simulations ([Bai et al. 2012](#)) do not suggest any clinically meaningful differences in exposure following fixed dose or dose adjusted for weight. A fixed dose of 1200 mg q3w was selected (equivalent to a body weight based dose of 15 mg/kg q3w) on the basis of this analysis.

4.1.3 Rationale for Radiotherapy Dose and Schedule

In the FORT Trial, a phase III randomized non-inferiority trial comparing low-dose radiotherapy (4 Gy in 2 fractions) and conventional dose radiotherapy (24 Gy in 12 fractions) in patients with follicular lymphoma or marginal zone lymphoma having local radiotherapy for definitive or palliative local control, low-dose radiotherapy (4Gy in 2 fractions) was associated with minimal toxicity and high rates of local tumor control (44.3% CR, 29.8% PR).⁴ In patients treated with an intratumoral TLR9 agonist, induction of circulating tumor reactive CTLs and responses at distant sites was only observed with concurrent low-dose, local radiotherapy with 4Gy in 2 fractions.⁵ This dose and fractionation is therefore safe and sufficient to induce both local disease control and a systemic immune response in patients with follicular lymphoma.

4.1.4 Rationale for Potential Treatment Beyond Progression

Cancer immunotherapy may result in early apparent radiographic progression (pseudoprogression/tumor immune infiltration), including the appearance of new lesions followed by delayed response ([Wolchok et al. 2009](#)). Additionally, responding tumors may appear to increase in size because of the influx of immune cells ([Hoos et al. 2010](#); [Pennock et al. 2012](#)). Unconventional response patterns have been described in patients treated with anti-CTLA-4 ([Wolchok et al. 2009](#)) and have been observed in the preliminary experience with atezolizumab in Study PCD4989g. This has led to the use of Modified RECIST criteria to account for potential pseudoprogression in clinical trials of MPLD3280A. Patients with CLL and NHL treated with the Bruton tyrosine kinase inhibitor ibrutinib or the PI3K inhibitor idelalisib have demonstrated reduction in adenopathy and clinical responses accompanied by transient lymphocytosis ([Davis and Letai 2012](#); [de Rooij et al. 2012](#); [Fiorcari et al. 2013](#)). Tumor flare in patients with lymphoma and CLL has been described in patients treated with lenalidomide ([Eve and Rule 2010](#); [Chanan-Khan et al. 2011](#)). This clinical response has been studied in vitro and is believed to be due to inhibition of B-cell receptor signaling and integrin

α 4 β 1 adhesion of malignant cells to fibronectin and VCAM-1. Current response criteria for lymphoma do not take into account such lymphocytosis, which is a phenomenon somewhat similar to the pseudoprogression described above in solid tumor patients. The potential for false-positive results on PET scans are also observed for patients with lymphoma.

4.2 Intervention

All patients will receive open-label atezolizumab 1200mg IV on day 1 (+/- 2 days) of a 21-day cycle for 1 year, for a planned total of up to 17 cycles of therapy. For patients assigned to receive atezolizumab and low-dose radiotherapy, 4Gy will be administered in 2 fractions to a single nodal site amenable to radiation as identified by the radiation oncologist on day 2 and day 3 of Cycle 1.

5.0 THERAPEUTIC/DIAGNOSTIC AGENTS

5.1 Study Drug: ATEZOLIZUMAB

Once marketing authorization is received commercial ATEZOLIZUMAB will be used and will not be provided by Genentech for "on-label" studies. For studies done before marketing authorization and/or "out of label", ATEZOLIZUMAB will be provided free of charge by Genentech but switched to commercial drug once marketing authorization is received. Genentech will replace any ATEZOLIZUMAB drug that is not reimbursed. For studies done "out of label," ATEZOLIZUMAB will be provided free of charge by Genentech. The Principal Investigator of the study will ensure maintenance of complete and accurate records of the receipt, dispensation, and disposal or return of all study drug in accordance with 21 Code of Federal Regulations (CFR), Part 312.57 and 312.62, and Genentech requirements.

5.1.1 Formulation

The ATEZOLIZUMAB drug product is provided in a single-use, 20-cc USP/Ph. Eur. Type 1 glass vial as a colorless-to-slightly-yellow, sterile, preservative-free clear liquid solution intended for IV administration. The vial is designed to deliver 20 mL (1200 mg) of ATEZOLIZUMAB solution but may contain more than the stated volume to enable delivery of the entire 20 mL volume. The ATEZOLIZUMAB drug product is formulated as 60 mg/mL ATEZOLIZUMAB in 20 mM histidine acetate, 120 mM sucrose, 0.04% polysorbate 20, pH 5.8.

ATEZOLIZUMAB must be refrigerated at 2°C – 8°C (36°F – 46°F) upon receipt until use. ATEZOLIZUMAB vials should not be used beyond the expiration date provided by the manufacturer. No preservative is used in the ATEZOLIZUMAB drug product; therefore, each vial is intended for single use only. Discard any unused portion of drug left in a vial. Vial contents should not be frozen or shaken and should be protected from direct sunlight.

For further details, see the ATEZOLIZUMAB Investigator's Brochure.

5.1.2 Dosage Administration, and Storage

The dose level of ATEZOLIZUMAB to be tested in this study is 1200 mg (equivalent to an average body weight based dose of 15 mg/kg) administered by IV infusion every 3 weeks (every 21 [\pm 2] days) for a total of 17 cycles. ATEZOLIZUMAB will be delivered in infusion bags with IV infusion

lines that have product contacting surfaces of polyvinyl chloride (PVC) or polyolefin and 0.2 μm in-line filters (filter membrane of polyethersulfone [PES]). No incompatibilities have been observed between ATEZOLIZUMAB and PVC or polyolefin infusion materials (bags or infusion lines).

Administration of ATEZOLIZUMAB will be performed in a setting with emergency medical facilities and staff who are trained to monitor for and respond to medical emergencies.

The initial dose of ATEZOLIZUMAB will be delivered over 60 (± 15) minutes. If the first infusion is tolerated without infusion-associated AEs, the second infusion may be delivered over 30 (± 10) minutes. If the 30-minute infusion is well tolerated, all subsequent infusions may be delivered over 30 (± 10) minutes. Vital signs should be collected within 60 minutes prior to each infusion and at the end of each infusion. Vital signs should be collected during the infusion only if clinically indicated. Patients will be informed about the possibility of delayed post-infusion symptoms and instructed to contact their study physician if they develop such symptoms.

No premedication will be allowed for the first dose of ATEZOLIZUMAB. Premedication may be administered for Cycles ≥ 2 at the discretion of the treating physician.

Guidelines for dosage modification, treatment interruption, or discontinuation and the management of specific adverse events are provided in Section 9.2 and Section 11.2.1, respectively.

5.2 Low- Dose, Local Radiotherapy

5.2.1 Simulation

Simulation techniques may vary based on the location of the site that needs to be treated. PET or CT simulation will be done as per radiation oncologist discretion.

Simulation should be done prior to radiation treatment start.

Typically, patients will be positioned in an immobilization device, which may vary depending on the site that needs to be treated. An Alpha Cradle, Aquaplast mold, facemask, or equivalent immobilization devices may be used. Alternatively, simulation can be done without the use of any immobilization at the discretion of the treating radiation oncologist.

IV and oral contrast may be used for simulation, unless the patient has an allergy that cannot be adequately pre-medicated.

Motion management, including but not limited to deep inspiration breath hold and 4D scans, can be used at the discretion of the treating radiation oncologist.

5.2.2 Treatment Planning

When available, an FDG-PET scan is preferred for treatment planning purposes and will be acquired on a flat tabletop when possible with the same immobilization devices used for the treatment planning CT simulation. MRI scans may also be acquired when deemed necessary by the treating radiation oncologist.

A 3D conventional radiotherapy (3D CRT) or intensity-modulated radiation treatment (IMRT) plan will be developed using Eclipse TM. Institutional standards for radiation quality assurance and radiation delivery will be used.

Either photons or electrons can be used at the discretion of the treating radiation oncologist.

The concept of ISRT (involved-site radiotherapy) as discussed in more detail in the ILROG guidelines will be used [4].

Modern RT planning in lymphoma incorporates the current concepts of volume determination as outlined in the ICRU Report 83 [5] based on defining a gross tumor volume (GTV) and clinical target volume (CTV) which is expanded to create a planning target volume (PTV). The PTV is then used to define dose coverage. This approach allows direct comparison with the diagnostic imaging, increasing the accuracy with which lymph node localization is defined.

The gross tumor volume (GTV) will be identified on the treatment planning CT and PET-CT or MRI when used. The attending radiation oncologist after reviewing the diagnostic CT, and other available imaging modalities when available will define the final GTV.

CTV encompasses in principle the original GTV with a 1-2cm margin, even if extended beyond the involved tissue or organ. Yet, normal structures such as lungs, kidneys, muscles that were clearly uninvolved, though previously displaced by the GTV, should be excluded from the CTV based on clinical judgment. In outlining the CTV the following points should be considered

- Quality and accuracy of imaging
- Concerns of changes in volume since imaging
- Spread patterns of the disease
- Potential sub-clinical involvement
- Adjacent organs constraints

If motion management techniques are used, at sites where respiratory motion is involved an ITV (internal target volume) will be defined. ITV is defined in the ICRU Report 62 as the CTV plus a margin taking into account uncertainties in size, shape, and position of the CTV within the patient. The ITV is mostly relevant when the target is moving, most commonly in the chest and upper abdomen with respiratory movements.

PTV is the volume that takes into account the CTV (and ITV, when relevant) and also accounts for set-up uncertainties in patient positioning and alignment of the beams during

treatment planning and through all treatment sessions. Typically, the expansion from CTV (or ITV when used) is 0.5cm.

The clinician and / or treatment planner adds the PTV and applies margins that depend on estimated set up variations that are a function of immobilization device, body site, and internal organ motion and patient cooperation. In general, margins for uncertainties, which are based on probability levels, should be added quadratically in order to avoid overly large margins based on the most extreme and least likely situations.

The Organs at Risk (OAR) are critical normal structures that can manifest adverse effects from radiation, usually dependent on the radiation dose and thus can influence treatment planning or the prescribed dose. They should be outlined on the simulation study. The planner should calculate dose

Volume Histograms (DVH) and the plan should be evaluated by the clinician in consideration of this information.

- Institutional dose-constraints guidelines will be met.

5.2.3 Treatment Delivery (LINAC- based)

All patients will receive a total of 400cGy delivered in two fractions, one fraction per day, on days 2 and 3 of cycle 1.

Initial positioning will be based on the initial simulation parameters and will be based on KV imaging with shifts to bony anatomy as appropriate.

Active monitoring of treatment delivery accuracy will be accomplished using KV imaging immediately before all treatment fields.

5.2.4 Study Medication Accountability

If study drug will be provided by Genentech, the recipient will acknowledge receipt of the drug by returning the INDRR-1 form indicating shipment content and condition. Damaged supplies will be replaced.

Accurate records of all study drug dispensed from and returned to the study site should be recorded by using the institution's drug inventory log or the National Cancer Institute drug accountability log.

All partially used or empty containers should be disposed of at the study site according to institutional standard operating procedure. Return unopened, expired, or unused study drug with the Inventory of Returned Clinical Material form as directed by Genentech.

6.0 CRITERIA FOR SUBJECT ELIGIBILITY

6.1 Subject Inclusion Criteria

Patients must meet the following criteria for study entry:

Signed Informed Consent Form (ICF)

Ability and willingness to comply with the requirements of the study protocol.

Age ≥ 18 years

Relapsed or refractory follicular lymphoma grade 1, 2, or 3A

- Relapsed disease is defined as having relapsed after greater than 6 months of prior treatment for follicular lymphoma
- Refractory disease is defined as failure to achieve a complete response or relapsed within 6 months of treatment for follicular lymphoma

Pretreatment biopsy for fresh tumor tissue collection is required

- If patient has recently undergone a biopsy and has not received any intercurrent anti-lymphoma therapy, archival tissue can be used

Stage III/IV disease

- Stage II disease is also eligible if disease is not encompassable within a single radiation field, as determined by the radiation oncologist.

At least one prior treatment for follicular lymphoma (no restriction to number or type of prior therapies)

- Patients treated for transformed diffuse large B cell lymphoma (DLBCL) who have retrograde transformation are eligible provided they have received at least one prior treatment for the follicular lymphoma

Site of disease amenable to low-dose, local radiotherapy (2 \times 2Gy), as recommended by the radiation oncologist.

At least one bi-dimensionally measurable lesion > 1.5 cm in its *longest diameter* by CT scan or magnetic resonance imaging as defined by the *Lugano Classification*

Adequate hematologic and end organ function:

- ANC ≥ 1500 cells/ μ L
 - If there is documented bone marrow involvement of follicular lymphoma, ANC must be ≥ 1000 cells/ μ L
- Platelet count $\geq 75,000$ μ L
 - If there is documented bone marrow involvement of follicular lymphoma, platelet count must be $\geq 50,000$ μ L
- Hemoglobin ≥ 9.0 g/dL
 - If there is documented bone marrow involvement of follicular lymphoma, hemoglobin must be ≥ 8.0 g/dL
- Total bilirubin $\leq 1.5 \times$ upper limit of normal (ULN)
 - Patients with known Gilbert disease who have serum bilirubin level $\leq 3 \times$ ULN may be enrolled.

- AST and ALT $\leq 3.0 \times$ ULN
 - Patients with liver involvement: AST and/or ALT $\leq 5 \times$ ULN
- Alkaline phosphatase $\leq 3 \times$ ULN
 - Patients with documented liver involvement or bone metastases: alkaline phosphatase $\leq 5 \times$ ULN
- Serum creatinine $\leq 1.5 \times$ ULN or creatinine clearance ≥ 30 mL/min on the basis of the Cockcroft-Gault glomerular filtration rate estimation:
 - $(140 - \text{age}) \times (\text{weight in kg}) \times (0.85 \text{ if female})$
 - $72 \times (\text{serum creatinine in mg/dL})$

For female patients of childbearing potential and male patients with partners of childbearing potential, agreement (by patient and/or partner) to use highly effective form(s) of contraception (i.e., one that results in a low failure rate [$< 1\%$ per year] when used consistently and correctly) and to continue its use for 5 months after the last dose of ATEZOLIZUMAB. Women must refrain from donating eggs during this same period.

- A woman is considered to be of childbearing potential if she is postmenarcheal, has not reached a postmenopausal state (≥ 12 continuous months of amenorrhea with no identified cause other than menopause), and is not permanently infertile due to surgery (i.e., removal of ovaries, fallopian tubes, and/or uterus) or another cause as determined by the investigator (e.g., Müllerian agenesis). The definition of childbearing potential may be adapted for alignment with local guidelines or regulations.
- Examples of contraceptive methods with a failure rate of $< 1\%$ per year include bilateral tubal ligation, male sterilization, hormonal contraceptives that inhibit ovulation, hormone-releasing intrauterine devices, and copper intrauterine devices.
- The reliability of sexual abstinence should be evaluated in relation to the duration of the clinical trial and the preferred and usual lifestyle of the patient. Periodic abstinence (e.g., calendar, ovulation, symptothermal, or postovulation methods) and withdrawal are not acceptable methods of contraception. If required per local guidelines or regulations, locally recognized acceptable methods of contraception and information about the reliability of abstinence will be described in the local Informed Consent Form.

Eastern Cooperative Oncology Group (ECOG) Performance Status of 0 or 1

Willingness to undergo on-treatment biopsies unless not clinically feasible while on treatment

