12.0 CRITERIA FOR THERAPEUTIC RESPONSE/OUTCOME ASSESSMENT

12.1 Tumor and Response Evaluation

Any evaluable or measurable disease must be documented at screening and reassessed at each subsequent tumor evaluation. Irradiated sites of disease, previously irradiated lesions, or lesions that are intended to be used to collect tissue samples for biopsy should not be counted as target lesions. Response will be assessed by the investigator per the *Lugano Classification* (Cheson et al, 2014; see Appendix 4) at tumor assessment timepoints (see Appendix 5).

Site of disease deemed amenable to low-dose, local radiotherapy (2 x 2Gy) should not be counted as target lesions.

Previously irradiated lesions should not be counted as target lesions.

Lesions that are intended to be used to collect tissue samples for biopsy should not be counted as target lesions.

Bone lesions should not be counted as target lesions.

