12.1.2 Primary Efficacy Outcome Measure

Objective response rate of atezolizumab alone and of atezolizumab with low-dose, local radiotherapy (objective response defined as CR or PR; as measured in non-irradiated sites of disease).

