14.3 Primary Efficacy Variables

Objective response is defined as a CR or PR, as determined by investigator assessment using *the Lugano Classification on Treatment Response Assessment Timepoints* (Appendix 4). Patients not meeting these criteria, including patients without any post-baseline tumor assessment, will be considered nonresponders in the analysis of objective response.

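### Entry guarantees one measurable lesion but not one that Section 12.1 allows as a target, so an eligible patient can be unscorable for CT-based partial response

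*Combined protocol and SAP*

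**What the plan says.** Section 6.1 sets three separate lesion requirements, for every patient and before the arm is known:

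- a measurable lesion: "At least one bi-dimensionally measurable lesion > 1.5 cm in its" longest diameter, by CT or MRI;
- a radiotherapy site: "Site of disease amenable to low-dose, local radiotherapy", as recommended by the radiation oncologist;
- tissue: "Pretreatment biopsy for fresh tumor tissue collection is required", with recent archival tissue accepted if no lymphoma therapy has intervened.

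It does not say that these must be different lesions. Disease must be stage III or IV, or else "Stage II disease is also eligible if disease is not encompassable within a single radiation field".

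Section 12.1 then restricts the target lesions. "Site of disease deemed amenable to low-dose, local radiotherapy (2 x 2Gy) should not be counted as target lesions", and "lesions that are intended to be used to collect tissue samples for biopsy should not be counted as target lesions". Previously irradiated lesions and bone lesions are also barred. The primary outcome in Section 12.1.2 is CR or PR, "as measured in non-irradiated sites of disease".

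Appendix 4 allows up to six target lesions and sets no minimum. It defines CT-based PR by the fall in SPD of the target lesions. Section 14.2 makes evaluability depend on treatment received, not on having a target. Section 14.3 adds: "Patients not meeting these criteria, including patients without any post-baseline tumor assessment, will be considered nonresponders in the analysis of objective response".

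**The concern.** The entry rule and the response rule do not meet. Entry secures one measurable lesion somewhere. The response rule may then remove that lesion from measurement, and no other section guarantees a replacement. The stage criterion implies disease beyond one radiation field, but not measurable disease there.

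At stake is whether the non-irradiated-site endpoint can be scored by both sets of criteria in every enrolled patient. Each arm is judged on a count of 9 responses in 25, so even one or two patients who are hard to score matter. Response is assessed by the investigator in an open-label trial, so it is better to settle which lesions count before the arm is known.

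**Working it through.** **Step 1. A patient who passes entry and has no target.** Take stage IV disease by marrow involvement, one 2.5 cm node, and other nodes of 1.5 cm or less. The 2.5 cm node is the measurable lesion and is also nominated for radiotherapy.

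| Rule | Result |
|---|---|
| 6.1 stage | met (stage IV) |
| 6.1 measurable lesion | met by the 2.5 cm node |
| 6.1 radiotherapy-amenable site | met by the same node |
| 12.1 radiotherapy-site bar | removes that node, in either arm |
| Other nodes | too small to be nodal targets |
| Permissible targets left | 0 |

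I read the Section 12.1 bar as applying to the one nominated site. If it covers every amenable site, more lesions are lost.

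**Step 2. What can still be scored, by visit (Appendix 5).**

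| Visit | Criteria reported | CT-based PR | PET-CT CR or PR |
|---|---|---|---|
| C5D1 | PET-CT and CT | not computable | possible if FDG-avid disease lies outside the field |
| C9D1, C13D1 | CT only | not computable | not available |
| End of treatment | PET-CT and CT | not computable | possible on the same condition |
| Follow-up | CT only | not computable | not available |

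**Step 3. How many sites are removed.** Section 10.1 (Laboratory/Pathology Assessments) directs the pretreatment biopsy to the site to be irradiated. Appendix 1 footnote f places the biopsy outside the radiation field. If the radiotherapy and biopsy sites are both measurable, one target is assured only with at least 1 + 1 = 2 measurable lesions when the sites coincide, and 2 + 1 = 3 when they differ. At least one of these must be neither bone nor previously irradiated. Entry asks for 1.

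**Step 4. The plan's own figures.** Inputs from Section 14.1: 25 per arm, promising at 9 or more responses, unpromising rate 0.20, promising rate 0.43, error rates 0.05 and 0.20. For X ~ Binomial(25, p), P(X ≥ 9) = Σ C(25, x) pˣ (1−p)²⁵⁻ˣ over x = 9 to 25.

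- p = 0.20: 0.0468, within the stated 0.05.
- p = 0.43: 0.8177, against the stated power of 0.80.

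The design reproduces and is not in dispute.

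**Step 5. Worst case.** Suppose k patients in an arm have no chance of being scored as responders. Then X ~ Binomial(25−k, p), still against a bar of 9. The documents give no k; 1 to 4 is an assumption.

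| k | P(X ≥ 9) at 43% | P(X ≥ 9) at 20% | Expected ORR, 0.43 × (25−k)/25 |
|---|---|---|---|
| 0 | 0.818 | 0.047 | 43.0% |
| 1 | 0.772 | 0.036 | 41.3% |
| 2 | 0.718 | 0.027 | 39.6% |
| 3 | 0.657 | 0.020 | 37.8% |
| 4 | 0.588 | 0.014 | 36.1% |

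If such patients keep some chance of response by PET-CT, power for a given k lies between the k = 0 row and the row for that k.

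**The case against.** The strongest reply is that response in this plan does not rest on target lesions alone, and most of that reply stands. PET-CT CR and PR in Appendix 4 use the uptake score and need no SPD. Section 14.5 takes the best response at any assessment timepoint, so a PET-CT response at C5D1 could count. Section 12.1 has all evaluable disease reassessed, Appendix 4 follows non-target lesions qualitatively, and a CT-based CR can be argued from non-measured disease that disappears.

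A reader might infer that a patient without a target has no lesion on which the primary endpoint can be measured and becomes a nonresponder by default. The documents do not support that. Section 14.3 makes a nonresponder only of someone who meets neither CR nor PR, and the patient in Step 1 could meet either by PET-CT if the marrow or small nodes are FDG-avid. The reply is nevertheless incomplete. The plan does not say that PET-CT alone decides when no SPD exists. For discordant PET-CT and CT results, Appendix 5 only recommends a further scan.

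A reader might also infer that the arms will differ because the nominated node would be measured in the atezolizumab-alone arm. Section 12.1 bars amenable sites whether or not they are irradiated, so that would be a breach of the plan and not a flaw in it.

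Nor do the documents show that three measurable lesions are generally needed. That holds only if the radiotherapy and biopsy sites differ and both are measurable. A biopsied lesion need not be measurable, and archival tissue may serve at baseline.

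Finally, advanced-stage disease probably makes the single-measurable-node case uncommon. That is reasonable, but the documents give no frequency either way.

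**Conclusion.** The gap is real and narrower than it first appears. Sections 6.1 and 12.1 together allow an eligible patient with no permissible target lesion, in either arm. For that patient CT-based PR cannot be computed at any visit, and the CT-only visits offer no PET-CT alternative. Response by PET-CT at C5D1 or end of treatment remains possible if FDG-avid disease lies outside the field.

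The power figures are an upper bound on the harm and not a forecast. They rest on an assumed k and on a zero chance of response in those patients. On that basis one such patient in an arm is enough to take power below the planned 0.80. The error is conservative: the risk is of missing a promising arm, not of falsely declaring one. This is a cheap improvement to eligibility, not a failure of the design.

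**What to change.** Amend the Section 6.1 criterion, for both arms, to require at least one bi-dimensionally measurable lesion over 1.5 cm that is permissible as a target under Section 12.1: outside the site nominated for radiotherapy, not the lesion to be biopsied, not previously irradiated and not in bone. Record the nominated radiotherapy site, the biopsy lesion and the target lesions on the eligibility checklist before randomisation.

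Reconcile Section 10.1 with Appendix 1 footnote f on where the biopsy is taken, because that determines whether one or two sites leave the target list.

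The cost is one criterion and a few checklist lines. Screening imaging, the radiation oncology consultation and the checklist already exist. The downside is that a few patients with a single measurable lesion become ineligible, which slows accrual slightly. A lesser alternative is to state how a patient with no target lesion is scored. That excludes nobody, but it leaves CT-based PR uncomputable in those patients.
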